**Clinically relevant non-major bleeding (CRNMB)**

Any sign or symptom of hemorrhage that does not fit into the definition of major bleeding, peri-partum major bleeding, postpartum major bleeding, or peri-partum minor bleeding, and meets at least one of the following criteria: requiring medical intervention by a health care professional, leading to hospitalization or increased level of care, prompting a face to face (not just telephone or electronic communication) evaluation. CRNMB will be sub-categorized into the antepartum and postpartum (24 hours-6 weeks postpartum) period.

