### **1.3 What are the risks with the standard of care regime of prophylactic LMWH/ASA?**

Downsides of LMWH include burden of injections (up to 400 injections/pregnancy), cost (\$4,000/pregnancy) and side effects of LMWH. In a systematic review of LMWH use in pregnancy, the most common side effects were bleeding (1.98%) which included significant antepartum bleeding, postpartum hemorrhage, and abdominal hematomas. Allergic skin reactions (1.8%) were also reported, some of which may be associated with HIT antibodies. Being on heparin lowers the likelihood that a woman receives epidural analgesia at the time of delivery, given the documented risk of epidural hematoma and associated hemiplegia when LMWH is not held prior to epidural analgesia. Serious and life-threatening complications of LMWH are rare, but possible. HIT has rarely been reported in pregnancy with the use of LMWH. The risk of osteoporosis and symptomatic fracture is rare, and significantly lower compared to unfractionated heparin.

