VTE is defined as symptomatic deep vein thrombosis (DVT) or pulmonary embolism (PE). DVT is defined as a non-compressible segment or filling defect proximal to the calf trifurcation based on ultrasonography, venography or magnetic resonance imaging. PE is diagnosed by a new intraluminal filling defect on CT pulmonary angiogram (segmental artery or more proximal), a high probability perfusion defect on a ventilation-perfusion study based on PIOPED criteria with planar images, or PE as a definite or probably cause of death.

Symptomatic ATE

Symptomatic arterial events include ischemic stroke, transient ischemic attack, myocardial infarction, peripheral embolism, or death due to a vascular cause based on autopsy findings (excluding PE or intracranial hemorrhage).

Major bleeding

Clinical or radiographical evidence of bleeding associated with one of: with a fall in hemoglobin of 20 g/L (2 g/dL) or more; or a requirement for transfusion of two or more units of red blood cells or whole blood; or symptomatic bleeding occurring in a critical site: intracranial, intraspinal, intraocular, pericardial, intra-articular, intramuscular with

compartment syndrome, or retroperitoneal, or was considered to have contributed to maternal death.

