**Non-major non-CRMN bleeding**

All other bleeding that does not fit into major bleeding, CRNMB, or peripartum bleeding.

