**Peripartum minor bleeding**

Hemorrhage occurring after the onset of labour or start of surgical delivery and within 24 hours postpartum that does not meet any criterion above and with estimated peripartum blood loss between 500 and 1000 ml.

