**Note that in view of this trial:**

- **Injection-site ecchymosis will not be reported as an AE.**
- **The following pregnancy-related symptoms will not be reported as an AE:**
  - **Nausea, vomiting**
  - **Minor vaginal bleeding**
  - **Gradual onset dyspnea**
  - **Fatigue**
  - **Bilateral leg, arm or facial swelling**
  - **Heart burn, weight gain, abdominal distension**

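### Bleeding that is part of a pregnancy loss can count as antepartum CRNMB, so the full trial's bleeding comparison mixes efficacy failures with other bleeding

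*Combined protocol and SAP*

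**What the plan says.** Section 2.6 defines CRNMB broadly: "Any sign or symptom of hemorrhage that does not fit into the definition of major bleeding, peri-partum major bleeding, postpartum major bleeding". Bleeds already graded as minor in the peripartum period are left out as well, and one further criterion has to be met. The criteria are medical intervention, hospital admission or a higher level of care, or a bleed "prompting a face to face (not just telephone or electronic communication) evaluation". On timing it says only: "CRNMB will be sub-categorized into the antepartum and postpartum (24 hours-6 weeks postpartum) period".

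The neighbouring classes in 2.6 are:

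- Major bleeding, which includes bleeding "with a fall in hemoglobin of 20 g/L (2 g/dL) or more". It has no exception for pregnancy loss.
- Peripartum bleeding, which runs from the onset of labour or the start of surgical delivery to 24 hours postpartum. The minor grade applies to a bleed that "does not meet any criterion above and with estimated peripartum blood loss between 500 and 1000 ml".
- The residual class: "All other bleeding that does not fit into major bleeding, CRNMB, or peripartum bleeding".

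Under Section 6.7 a blinded committee decides whether suspected bleeding meets the protocol's outcome criteria. Section 8.1.4 compares each bleeding outcome between arms by intention to treat with an unadjusted Fisher's test. It adds pilot data to the full-trial analysis if the design does not change significantly.

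Section 7.3 states "Injection-site ecchymosis will not be reported as an AE" and also exempts minor vaginal bleeding. Both exemptions concern adverse-event reporting. Section 2.6 does not repeat them.

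**The concern.** A woman with prior losses who bleeds during a miscarriage and is examined or treated for it meets the CRNMB wording, unless the bleed is severe enough to be major or falls under the peripartum classes. An early loss would not normally reach the peripartum classes, which start with labour or surgical delivery and need at least 500 ml for the minor grade. Adjudicators are asked to apply the written criteria, so they have no stated basis for setting such a bleed aside.

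The same event can therefore be a failure on the primary full-trial outcome and a bleed on a safety outcome. Any difference between arms in pregnancy loss then carries into the CRNMB difference. The full trial asks whether LMWH can be dropped, and bleeding is one of the downsides of LMWH listed in Section 1.3, so the bleeding comparison needs to be interpretable alongside the live birth result.

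The residual class has a smaller ambiguity. Read literally, it includes injection-site bruising, which only women receiving injections can have.

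**Working it through.** **Planning scenario.** Section 8.2 gives 60% in the ASA arm, a 10-point difference, 80% power, alpha 0.05, 10% drop-out and 828 participants. Taking 60% vs 70% live birth, two-sided:

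- Uncorrected n per arm = [1.96·√(2·0.65·0.35) + 0.8416·√(0.60·0.40 + 0.70·0.30)]² / 0.10² = 356.
- With continuity correction: 376 per arm.
- With 10% added: 376 × 1.10 = 413.6, so 414 per arm and 828 in total.

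This matches the plan. Sixty vs 50% does not, so losses of 40% on ASA and 30% on LMWH/ASA are the scenario behind the stated size. Equal allocation is assumed; the ratio is not stated.

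**Loss-related CRNMB alone.** Let f be the share of losses whose bleeding qualifies. The documents do not give f, so it is ranged. The gap between arms is f × (40 − 30) points:

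- f = 25%: 10.0% vs 7.5%, gap 2.5 points
- f = 50%: 20% vs 15%, gap 5 points
- f = 100%: 40% vs 30%, gap 10 points

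**With other bleeding added.** Let b be CRNMB unrelated to loss and e the true LMWH excess, both assumed.

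- ASA risk = 1 − (1 − b)(1 − 0.40f)
- LMWH/ASA risk = 1 − (1 − b − e)(1 − 0.30f)

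Observed CRNMB, ASA vs LMWH/ASA (difference in points):

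| b, e | f = 0 | f = 25% | f = 50% | f = 100% |
|---|---|---|---|---|
| 2%, 1.98% | 2.0 vs 4.0 (+2.0) | 11.8 vs 11.2 (−0.6) | 21.6 vs 18.4 (−3.2) | 41.2 vs 32.8 (−8.4) |
| 5%, 5% | 5.0 vs 10.0 (+5.0) | 14.5 vs 16.8 (+2.3) | 24.0 vs 23.5 (−0.5) | 43.0 vs 37.0 (−6.0) |
| 5%, 10% | 5.0 vs 15.0 (+10.0) | 14.5 vs 21.4 (+6.9) | 24.0 vs 27.8 (+3.8) | 43.0 vs 40.5 (−2.5) |

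The excess is exactly cancelled where the two risks are equal. For the middle row, 0.95 − 0.38f = 0.90 − 0.27f, so f = 0.05/0.11 = 45%. For the first and third rows f is 19% and 80%.

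**Dependence on the loss difference.** Take b = 5%, e = 5%, f = 50% and 40% loss on ASA. Power is for a significant result showing harm from LMWH (two-sided Fisher's test, 376 per arm, 3,000 simulated trials).

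| Loss on LMWH/ASA | Observed CRNMB | Difference | Risk ratio | Power |
|---|---|---|---|---|
| Loss bleeds excluded (f = 0) | 5.0 vs 10.0 | +5.0 | 2.00 | about 70% |
| 30% | 24.0 vs 23.5 | −0.5 | 0.98 | about 1.5% |
| 40% (equal) | 24.0 vs 28.0 | +4.0 | 1.17 | about 21% |
| 50% | 24.0 vs 32.5 | +8.5 | 1.35 | about 70% |

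In the last row the risk difference is exaggerated, from 5 to 8.5 points.

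**Smaller loss differences.** The two LMWH/ASA trials described in Section 1.1 report live birth of 78% vs 72% and 77% vs 75%. These are loss gaps of 6 and 2 points. At f = 25% they give 1.5 and 0.5 points of CRNMB; at f = 50%, 3.0 and 1.0.

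**The case against.** A reader might infer that every loss is also an antepartum CRNMB. The documents do not support that. A loss without bleeding that is evaluated or treated does not qualify, and Section 7.5 itself recognises missed abortion. A loss with a haemoglobin fall of 20 g/L is major bleeding, which CRNMB excludes. A later loss with labour or surgical delivery can fall under the peripartum classes. So f is unknown and probably below 100%.

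A reader might also set the gaps against the 1.98% bleeding rate in Section 1.3. That figure is a rate on LMWH from a systematic review and includes postpartum haemorrhage and abdominal haematomas. It is neither an excess over ASA nor a CRNMB rate. It appears in the first table row only as one assumed size of excess.

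Three further points carry weight:

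- Counting all bleeding whatever its cause is defensible in an open-label trial, because it avoids causal attribution. This supports keeping the inclusive count, but not reporting it alone.
- Loss and its gestational age are recorded and bleeding is adjudicated blind, so a later split is possible. Without a field for it, that means going back to the records.
- The pilot has 24 participants and its feasibility analyses contain no bleeding outcome. At about 12 per arm, 5 points is 0.6 of an event.

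Injection-site bruising is a consequence of LMWH injections, so counting it is not wrong in itself. The plan needs only to say whether it counts.

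**Conclusion.** The gap in wording is real and no other section closes it. Bleeding that is part of a loss and is evaluated in person or treated counts as antepartum CRNMB unless it is major or peripartum, and the planned comparison does not separate it. Major bleeding has the same gap.

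Under the 60% vs 70% scenario the distortion is 2.5 to 10 points against ASA for f from 25% to 100%, enough to mask or reverse an LMWH excess of plausible size. It would be wrong to conclude that the plan hides the bleeding cost of LMWH whatever happens. Masking or reversal needs fewer losses on LMWH/ASA; equal losses only dilute the contrast, and more losses on LMWH/ASA push the difference the other way. The values of f, b and e are assumptions.

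The point concerns a secondary safety outcome of the full trial, collected in the pilot for possible pooling. It does not touch the pilot's feasibility endpoints.

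**What to change.** - Keep the severity definitions and thresholds in 2.6 as they are. Moving loss-related bleeds to the peripartum scale would be a mistake: a 20 g/L fall that is major now could lose that grade, since peripartum major bleeding asks for 40 g/L or another criterion, and a bleed under 500 ml might have no grade.
- Add one field to the bleeding and adjudication forms, from the pilot onward, marking a bleed as part of a pregnancy loss. The blinded committee in 6.7 confirms it.
- In 8.1.4, compare antepartum CRNMB and major bleeding between arms both excluding and including flagged bleeds. Report flagged bleeds by arm at their existing grade.
- Reconcile the residual bleeding class in 2.6 with the notes in 7.3: state whether injection-site ecchymosis and minor vaginal bleeding count there, or tabulate injection-site ecchymosis separately.

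The cost is one form field and a few table rows. The excluding-loss analysis depends on attributing a post-randomisation event, even if blinded, so the inclusive count must stand beside it.

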**Non-major non-CRMN bleeding**

All other bleeding that does not fit into major bleeding, CRNMB, or peripartum bleeding.

**Peripartum major bleeding**

Hemorrhage occurring after the onset of labour or start of surgical delivery and within 24 hours postpartum that meets at least one of the following: necessitating a surgical procedure, or associated with a fall in hemoglobin of 40 g/L (4 g/dL) or more, or a requirement for transfusion of two or more units of red blood cells or whole blood, or estimated peripartum blood loss >1000 ml, or considered to have contributed to maternal death.

**Peripartum minor bleeding**

Hemorrhage occurring after the onset of labour or start of surgical delivery and within 24 hours postpartum that does not meet any criterion above and with estimated peripartum blood loss between 500 and 1000 ml.

**HIT**

Heparin-induced thrombocytopenia (HIT) is defined as a clinical diagnosis of HIT (based on a 4T score that is intermediate or high probability) and a minimum of a positive PF4 HIT ELISA assay.

**Symptomatic Fracture**

A symptomatic fracture confirmed by radiography.

**Allergic reaction**

A reaction following the administration of LMWH that results in anaphylaxis or a rash requiring discontinuation of the allocated LMWH.

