### **2.3 Pilot Trial Endpoints**

The primary feasibility outcome of the pilot trial is a mean recruitment rate of 0.5 subjects per center per month. The secondary feasibility outcomes of the pilot trial and associated *a priori* feasibility targets are as follows:

1. Proportion of sites requiring >18 months to obtain all required approvals/contracts from time of delivery of all study documents: <50%.
2. Proportion of screened patients who meet eligibility criteria (i.e. patients who meet inclusion criteria and are also eligible based on exclusion criteria): >30% of subjects
3. Proportion of eligible subjects who provide consent: >30% of subjects
4. Proportion of withdrawals/loss to follow-up among randomized patients: <10% of subjects
5. Crossover rate between standard of care and experimental study arms: <20%
6. Level of compliance with study drug: >80% compliance rate of total antepartum LMWH use
7. Reasons for physician and patient non-consent

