**5.4 Study drug management**

The study drug (ASA and LMWH) will be dispensed by the local site hospital Pharmacy Department for all participants in both treatment arms. The local site hospital Pharmacy Department will be responsible for labeling, handling, and dispensing of the study drug.

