#### **8.1.4. Full Trial Analyses**

Several secondary outcomes will be collected in the pilot trial, which will be included in the analysis of the full trial if there are no significant changes to the trial design.

**Primary analysis:** Analysis will be performed by intention to treat. Intention to treat analysis will be supplemented by a sensitivity analysis that excludes subjects who did not complete the allocated treatment plan. The live birth rate will be compared in the experimental and standard of care arm by an unadjusted Fisher's test of proportions, with 95% confidence intervals provided.

**Secondary analysis:** Analysis will be performed by intention to treat. Intention to treat analysis will be supplemented by a sensitivity analysis that excludes subjects who did not complete the allocated treatment plan. Proportions will be compared between study arms by an unadjusted Fisher's test, with 95% confidence intervals reported. The following outcomes will be analyzed: Pregnancy loss by central laboratory testing, pregnancy loss by gestational age (<10 weeks, 10-19 weeks,  $\geq$ 20 weeks gestation), pre-eclampsia, early onset pre-eclampsia, severe pre-eclampsia, SGA <10th percentile, SGA <5th percentile, SGA <3rd percentile, placental abruption requiring delivery, pre-term delivery <37 weeks gestation, symptomatic VTE, symptomatic ATE, major bleeding, clinically relevant non-major bleeding, non-major non-CRNMB, major peripartum bleeding, minor peripartum bleeding, HIT, symptomatic fracture, allergic reaction, and all-cause mortality.

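### A rash counts as an allergic reaction only if it stops the allocated LMWH, so the same LMWH rash can count in one arm and not in the other

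*Combined protocol and SAP*

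**What the plan says.** Section 2.6 gives allergic reaction two limbs, both after LMWH: "A reaction following the administration of LMWH that results in anaphylaxis or a rash requiring discontinuation of the allocated LMWH". HIT, in the same section, needs an intermediate or high 4T score and a positive PF4 assay, and does not refer to the treatment allocated.

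Section 8.1.4 lists both outcomes for the full trial ("HIT, symptomatic fracture, allergic reaction, and all-cause mortality"). The rule for secondary outcomes is "Analysis will be performed by intention to treat", and "Proportions will be compared between study arms by an unadjusted Fisher's test, with 95% confidence intervals reported". A sensitivity analysis leaves out women who did not complete their allocated plan.

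The experimental arm is aspirin alone (Synopsis; sections 3.1 and 5.1). Section 5.4 treats both agents as study drug: "The study drug (ASA and LMWH) will be dispensed by the local site hospital Pharmacy Department for all participants in both treatment arms". Women in the aspirin arm can still receive LMWH. Section 2.3 sets a crossover target, "Crossover rate between standard of care and experimental study arms: <20" per cent. Section 3.6 has crossover and its reasons documented, and section 3.5 leaves postpartum LMWH to the treating physician.

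**The concern.** An outcome compared between randomised arms should be ascertained by the same rule in each. Here the word *allocated* ties the rash limb to the randomised assignment. The same clinical event, LMWH stopped because of a rash, is an endpoint in one arm and not in the other.

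The definition also leaves out every reaction to aspirin, although the full trial's stated purpose includes the safety of aspirin alone. The listed allergic-reaction rate for the experimental regimen would thus be low partly because of how the outcome is worded. A reader of the results table could not tell how much of the contrast is real avoidance of LMWH harm and how much is the definition.

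**Working it through.** **Reading the definitions against the arms**

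| Event | LMWH/aspirin arm | Aspirin arm |
|---|---|---|
| Rash, antenatal LMWH stopped | Counts | Does not count: no LMWH was allocated |
| Anaphylaxis after LMWH | Counts | Counts on the natural reading, if she received LMWH |
| Rash or anaphylaxis from aspirin | Does not count | Does not count |
| HIT | Counts | Counts, if she received LMWH |

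The asymmetry is clearest for antenatal crossover. For postpartum LMWH, it is not stated whether the drug is still the allocated one even in the LMWH/aspirin arm, since allocation there runs to 37 weeks or the onset of labour.

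**Arm size.** Section 8.2 gives 828 from 60% v 70%, 80% power, alpha 0.05 and 10% dropout. Two-sided testing and 1:1 allocation are assumed.
- Uncorrected: n = [1.96√(2×0.65×0.35) + 0.8416√(0.6×0.4 + 0.7×0.3)]² / 0.10² = 356 per arm.
- With continuity correction: 376 per arm.
- 376 × 1.1 = 413.6, rounded up to 414 per arm, or 828. The plan's figure reproduces.

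**Expected events (illustration).** The documents give no rate for this endpoint. Section 1.3 gives 1.8% for allergic skin reactions on LMWH. That category is broader than anaphylaxis or a rash that stops treatment, so 1.8% is an assumption and probably high. Half of it is shown for range. Crossover into LMWH of 10% and 20% is also assumed, up to the limit of the section 2.3 target, and each crossed-over woman is given the full risk.

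| | 1.8% | 0.9% |
|---|---|---|
| LMWH/aspirin arm, all 414 exposed | 0.018 × 414 = 7.5 | 3.7 |
| Aspirin arm, 10% exposed (41.4 women) | 0.018 × 41.4 = 0.7 | 0.4 |
| Aspirin arm, 20% exposed (82.8 women) | 0.018 × 82.8 = 1.5 | 0.7 |

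The aspirin-arm rows are reactions expected to occur. Those that are rashes go uncounted.

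**Effect on the test.** With 414 per arm, two-sided Fisher gives p = 0.062 for 5 v 0, 0.031 for 6 v 0 and 0.015 for 7 v 0. At 1.8% in the LMWH/aspirin arm and zero in the aspirin arm, the chance of p ≤ 0.05 is about 76%. If reactions in LMWH-exposed aspirin-arm women were counted, it would be about 56% at 10% crossover and 39% at 20%. This takes all reactions as rashes, crossover as one-way, and no aspirin reactions, so it is the most the wording could matter under these rates.

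**Pilot.** With about 12 women per arm, 0.018 × 12 = 0.2 events are expected. No pilot conclusion turns on this endpoint.

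**The case against.** The strongest reply is that the low aspirin-arm rate is mostly real. A woman who never receives LMWH cannot react to it, and sparing women LMWH harms is part of the case for aspirin alone in section 1.3. An endpoint specific to LMWH is a defensible choice. This stands: a 7 v 0 result would mainly show true LMWH harm and would not be a false finding.

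Second, the uncounted events are not lost. Sections 7.1, 7.3 and 7.4 make suspected medication reactions adverse events and ask for a judgement on their relation to study and concomitant drugs, and section 4.3 has all safety data analysed. This also stands, but it preserves the raw data without correcting the endpoint listed in section 8.1.4. The sensitivity analysis does not correct it either. It removes crossovers without restoring their rashes, and on its plain terms could also remove a woman who stopped LMWH because of a rash.

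Third, a reader might infer that the aspirin arm scores exactly 0% by definition. The text does not support that. The discontinuation condition naturally attaches to the rash only, so anaphylaxis after crossover or postpartum LMWH could count.

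Fourth, a reader might infer that counting HIT in a crossed-over woman against the aspirin arm is an error. It is ordinary intention-to-treat attribution. The fault is only that rash in the same woman is handled differently.

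**Conclusion.** The point holds as an arm-dependent outcome definition. Followed as written, an LMWH rash counts or not according to allocation, HIT follows another rule, and aspirin reactions count nowhere. The aspirin-arm rate is therefore at or near zero partly by definition.

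The documents do not support calling the whole contrast an artefact. The discrepancy is about 0.7 to 1.5 reactions at most in 414 women, if the 1.8% rate applies and 10% to 20% cross over into LMWH, and about half that at a 0.9% rate.

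Severity is low. This is one of 21 secondary outcomes of the full trial, and no pilot feasibility target or stopping rule depends on it. It is worth settling now because section 8.1.4 carries pilot outcomes into the full-trial analysis if the design does not change significantly. A later change could leave two definitions in one dataset.

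**What to change.** In section 2.6, define allergic reaction as anaphylaxis, or a rash requiring discontinuation, attributed to study drug (aspirin or any LMWH received), regardless of allocation. Say expressly that the discontinuation condition applies to rash only, and record the suspected drug.

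In section 8.1.4, keep the intention-to-treat comparison of allergic reaction and of HIT by randomised arm, and state that both are attributed by this one rule. Removing them from the randomised comparison is not needed, since an exposed-only group is defined after randomisation. Instead, add a descriptive summary, as proportions with 95% confidence intervals, of LMWH-attributed reactions and HIT among women who received LMWH after randomisation.

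The cost is a revised definition, a short addition to the analysis section and one data field. Section 7.4 already asks the investigator to judge drug relationship, and section 3.6 already documents crossover. The small downside is that aspirin reactions, expected to be similar in both arms, slightly dilute the overall contrast. The breakdown by suspected drug deals with that.
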